6 STATISTICAL METHODS

6.1 Statistical and Analytical Plans

Tabular summaries of the data collected during the study will be presented to provide a general description of the subjects studied and an overview of the Efficacy, PK and safety results. Data from all sites will be combined in the computation of these summaries and summaries will be presented by treatment group. Continuous variables will be summarized using descriptive statistics (number of subjects, mean, standard deviation [SD], median, and minimum and maximum values). Categorical (nominal) variables will be summarized using frequency tables (number and percentage of subjects in each category).

In addition to tabular summaries, subject data listings, as specified in Sections 16.2 and 16.4 of ICH Guidance E3, will be provided. Additional subject data listings to be provided for this study are listed under the relevant subsections below. All data analyses will be performed by the CRO after the study is completed and the database is released. Statistical programming and analyses will be performed using SAS® and/or other validated statistical software as required.

Complete details of the statistical analysis will be provided in a separate statistical analysis plan (SAP), which will be written, finalized, and approved prior to database lock and will be included in the Clinical Study Report (CSR) for this protocol. The statistical analysis plan will supersede the statistical analysis methods described in this clinical protocol. Any deviation from the statistical plan will be documented and described in the final report. If changes to principal features stated in the protocol are required, these will be documented in a protocol amendment. The final SAP will take into account any amendment to the protocol.

In general, the baseline value for a variable is defined as the last observation prior to the first dose of double-blind study medication, ideally Visit 3, but including the screening value, if necessary.

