| 3.5 | 17 | A paragraph is added to describe the changes in the sample size and randomization scheme after the planned interim analysis and the new blinded SD estimate. | Protocol amendment V9.0 Note the effect of sample size increase on the type-I error is controlled by the method of inverse normal p-value combination test (MINP) (Section 6.5.7) |
| 4 | 18 | Added “Baseline Period”, “Titration Period”, “Maintenance Period”, and “Treatment Period” definitions | Clarification |
| 5.1 | 19 | A clarification of the visit range is added for the treatment period | Clarification |
| 5.2 | 20-21 | 
 a. Added “at Visit 6” to clarify caregiver’s timing for CGI-I | Clarification |

| | | | |
|-------|----|---|--|
| | | b. Added “Oppositional defiant disorder” to SNAP-IV ADHD scores c. Protocol Appendix numbers are updated in this section and various sections thereafter. This same description will not be repeated Descriptions for CHQ-PF28 are updated to include reference for the derivation of scores for individual items, multi-item scales, and summaries | Clarification and correction is made to the CHQ-PF28 scoring based on the published manual |
| 5.3 | 22 | Previous Section “5.3 Pharmacokinetic Variables” is removed | PK analysis is not the scope of this SAP |
| 5.4.7 | 23 | Visit range for C-SSRS is corrected | Administrative |
| 5.4.8 | 24 | “by the site coordinator” is added to clarify the subjects who administer the caregivers’s assessment of patient’s IA daily activities | Clarification |
| 5.4.9 | 24 | Inserted sentences describing the ranges of the scale scores | Clarification |
| 6.1 | 25 | Respecified the number of decimal places for some summary statistics in the table presentation | Administrative |
| 6.2 | 26 | Clarified how unscheduled data points will be used in the analysis | Clarification |
| 6.3 | 26 | Updated the reference for the statistical method and added two more covariates for the adjustment of covariates: pooled site and baseline IA adjusted to 7 days | Administrative |
| 6.4 | 28 | Expanded text to include methods of deriving weekly IA frequency in the treatment and maintenance period when subject discontinued the study or date of last dose is missing; Replaced LOCF analysis with MMRM analysis for secondary endpoints | To provide detail of how primary endpoint is calculated when diary and dosing data are incomplete replace LOCF method by MMRM with respect to secondary endpoints |

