6.5.6 Adaptation Rules

Based on the conditional power calculated in Section 6.5.5, the independent statistician will use the following adaptation rules for sample size adjustment and make recommendation to the sponsor.

Table 2. Sample Size Adjustment Decision Rules

| Case | Dose 1 (█ mg) | Dose 2 (█ mg) | Decision for Stage 2 Sample Size Adjustment | Verbiage for Communication to Sponsor (Section 6.5.8) |
|------|---|---|--|--|
| 1 | $Cp_L < 10\%$ | $CP_H < 10\%$ | Terminate the trial. | CASE 1. Terminate the trial. |
| 2 | $Cp_L < 10\%$ | $10\% \leq CP_H \leq 36\%$ or $CP_H > 80\%$ | Subjects to be randomized to Dose 1 group in Stage 2 will be allocated to Dose 2 and Placebo groups; However, subjects who received dose 1 prior to the interim analysis will continue to receive dose 1 in Stage 2. | CASE 2. Stop enrollment for █ mg group, allocate Stage 2 planned █ mg sample size to █ mg and Placebo. |
| 3 | $10\% \leq CP_L \leq 36\%$ or $CP_L > 80\%$ | $CP_H < 10\%$ | Subjects to be randomized to Dose 2 group in Stage 2 will be allocated to Dose 1 and Placebo groups; However, subjects who received Dose 2 prior to the interim analysis will continue to receive Dose 2 in Stage 2. | CASE 3. Stop enrollment for █ mg group, allocate Stage 2 planned █ mg sample size to █ mg and Placebo. |
| 4 | $Cp_L < 10\%$ | $36\% < CP_H \leq 80\%$ | 
Enrollment for Dose 1 group will be terminated. Sample size in Dose 2 and Placebo groups will be increased to achieve the conditional power of at least 90% (before the multiplicity adjustment). This increase will include subjects allocated to Dose 2 and Placebo from Dose 1 termination
 
The maximum increase will not result in the doubling of the total sample size. In other words, suppose n_1 and n_2 are the sample sizes per arm at the interim analysis and n_{2adj} is the calculated adjusted sample size. If $(n_1 + n_{2adj}) \leq 2 * (n_1 + n_2)$ then the adjusted sample size for Stage 2 will be n_{2adj} as calculated. If $((n_1 + n_{2adj}) > 2 * (n_1 + n_2))$ then $n_{2adj} = 2 * (n_1 + n_2) - n_1$.
 | CASE 4. Stop enrollment for █ mg group, increase Stage 2 sample sizes for █ mg and Placebo to xxx/group. |

| Case | Dose 1 (█ mg) | Dose 2 █ mg) | Decision for Stage 2 Sample Size Adjustment | Verbiage for Communication to Sponsor (Section 6.5.8) |
|------|--|--|---|--|

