$$= \frac{n_1}{Z_{1-p_1}^2} \left\{ \frac{1}{\sqrt{w_2}} (Z_{1-\alpha_2} - \sqrt{w_1} Z_{1-p_1}) - \Phi^{-1}(1 - CP) \right\}^2.$$

The following rules will be applied to compute the sample sizes across the treatment arms in Stage 2:

- If a decision to discontinue subject enrollment is made for a particular dosing arm at Interim Analysis, subjects who were planned to be enrolled in that arm after Interim Analysis will be re-distributed to the remaining treatment arms. For example, if Dose 1 is dropped and Dose 2 is retained, the sample sizes for the three treatment arms in Stage 2 will be defined as follows:
 - Dose 1: 0
 - Dose 2: $n_{22} + n_{21} / 2$
 - Placebo: $n_{23} + n_{21} / 2$

where n_{ij} is the sample size allocated to Stage i for Treatment Group j .

- If a decision is made to increase the sample size in at least one dosing arm, the modified sample size in the placebo arm will be equal to the larger modified sample size in the two dosing arms. For example, if the modified sample sizes in the two dosing arms in Stage 2 are n_{31} and n_{32} , respectively, the modified sample size in the placebo arm in Stage 2 will be set to $\max(n_{31}, n_{32})$. However, if the sample size is increased in one dosing arm, the sample size in the other dosing arm will not be automatically increased.

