6.5.7 Adaptive Design

This section defines the mathematical approach used in the proposed adaptive design with two stages and data-driven decision rules (e.g., sample size modification at Interim Analysis). The derivation of the adaptive design is based on the combination function approach applied in conjunction with the closure principle, see, for example, Wang et al. (2001), Brannath et al. (2002) and Hommel (2005). This general approach is commonly used to construct adaptive designs in confirmatory trials and guarantees that the overall Type I error rate is protected in the trial at the nominal level (two-sided $\alpha = 0.05$) regardless of the type of design modifications at an Interim Analysis, including decisions to drop a treatment arm or adjust the sample size in one or more arms.

Let H_1 and H_2 denote the null hypotheses of no treatment effect for the two dose-placebo comparisons (Dose 1 versus placebo and Dose 2 versus placebo). According to the combination function approach, the amount of evidence to reject these null hypotheses will be evaluated separately in each individual stage of the trial and the inferences at the final analysis will be performed by combining the evidence across the two stages. Further, the rejection rules for H_1 and H_2 will be chosen to achieve consistency with the Hochberg procedure (Dmitrienko and D'Agostino, 2013) that was pre-defined as multiplicity adjustment tool in this trial. To achieve this consistency, the Hochberg procedure will be applied within each stage (Hochberg, 1988).

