Let p_i and q_i denote the p-values for testing the null hypothesis H_i , $i = 1, 2$, based on the data in Stages 1 and 2, respectively. The Stage 2 p-values are computed from the samples obtained after Interim Analysis, i.e., the sample size in a dosing arm may be adjusted as explained above. Further, $p_{(1)} < p_{(2)}$ will denote the ordered treatment effect p-values in Stage 1 and similarly $q_{(1)} < q_{(2)}$ will denote the ordered treatment effect p-values in Stage 2. These p-values will be used to construct a closure-based representation of the Hochberg procedure in each of the two stages. To define the closure-based representation, a closed family of intersection hypotheses that includes all possible non-empty intersections of the two null hypotheses will be set up. Table 3 and Table 4 display the intersection hypotheses in the closed family and associated intersection p-values that define the Hochberg procedure in Stage 1 and Stage 2 respectively.

Table 3: Intersection hypothesis and Hochberg intersection p-values in Stage 1

| Intersection hypothesis | Hochberg intersection p-value |
|-------------------------|--------------------------------------|
| $H_1 \cap H_2$ | $p_{12} = \min (2 p_{(1)}, p_{(2)})$ |
| H_1 | p_1 |
| H_2 | p_2 |

Table 4: Intersection hypothesis and Hochberg intersection p-values in Stage 2

| Intersection hypothesis | Hochberg intersection p-value |
|-------------------------|--------------------------------------|
| $H_1 \cap H_2$ | $q_{12} = \min (2 q_{(1)}, q_{(2)})$ |
| H_1 | q_1 |
| H_2 | q_2 |

Note that, if a certain dose is dropped due to futility at Interim Analysis, the corresponding p-values in Stage 2 is automatically set to 1 to remove the dosing arm from consideration. This guarantees that a null hypothesis cannot be rejected at Final Analysis if the corresponding dose was dropped due to futility at Interim Analysis. Further, the p-values computed at Interim Analysis (Stage 1 p-values) are not used for inferential purposes and therefore no α will be spent at Interim Analysis to stop the trial early due to overwhelming efficacy.

As an illustration, if Dose 1 is dropped at Interim Analysis, the corresponding treatment effect p-value in Stage 2 (q_1) will be set to 1. As a result, the intersection p-values will be defined in Stage 2 as shown in Table 5 (note that the smaller ordered p-value will be equal to q_2 and the larger ordered p-value will be equal to 1).

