Table 5: Intersection hypotheses and Hochberg intersection p-values in Stage 2 if dose 1 is dropped at Interim Analysis

| Intersection hypothesis | Hochberg intersection p-value |
|-------------------------|-------------------------------|
| $H_1 \cap H_2$ | $q_{12} = \min(2 q_2, 1)$ |
| H_1 | 1 |
| H_2 | q_2 |

The inferences for the two null hypotheses will be performed at final analysis using the composite treatment effect p-values that will be defined as follows. Let w_1 and w_2 define the stage weights that are prospectively defined based on the expected amount of information at Interim Analysis. Since Interim Analysis is planned to be taken after 50% of the subjects have completed the trial, n_1 (total sample size in Stage 1) and n_2 (total sample size in Stage 2 before sample size adjustment), and thus the pre-specified stage weights are given by

$$w_1 = \frac{n_1}{n_1 + n_2} = 0.5, w_2 = \frac{n_2}{n_1 + n_2} = 0.5.$$

Using the stage weights, the combination function to be used at Final Analysis will be defined as follows:

$$c(x_1, x_2) = 1 - \Phi[\sqrt{w_1}\Phi^{-1}(1 - x_1) + \sqrt{w_2}\Phi^{-1}(1 - x_2)],$$

where $\Phi(x)$ is the cumulative distribution function of the standard normal distribution.

This combination function will be applied to compute composite intersection p-values for each intersection hypothesis in the closed family. The resulting composite intersection p-values are denoted by r_{12} , r_1 , r_2 , and are defined in Table 6.

Table 6: Intersection hypothesis and composite intersection p-values at final analysis

| Intersection hypothesis | Composite intersection p-value |
|-------------------------|--------------------------------|
| $H_1 \cap H_2$ | $r_{12} = c(p_{12}, q_{12})$ |
| H_1 | $r_1 = c(p_1, q_1)$ |
| H_2 | $r_2 = c(p_2, q_2)$ |

After that, the null hypothesis H_1 will be rejected at Final Analysis (which implies a statistically significant treatment effect at Dose 1) if the composite p-values for all intersection hypotheses in the closed family that contain H_1 are significant at $\alpha = 0.05$ (two-sided), i.e.,

$$r_{12} \leq \alpha \text{ and } r_1 \leq \alpha.$$

Similarly, the null hypothesis H_2 will be rejected at Final Analysis (and a statistically significant treatment effect will be established at Dose 2) if the composite p-values for all intersection hypotheses in the closed family that contain H_2 are significant at $\alpha = 0.05$, i.e.,

$$r_{12} \leq \alpha \text{ and } r_2 \leq \alpha.$$

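### After one dose is dropped at the interim, the intersection test still doubles the surviving dose's Stage 2 p-value: valid, but it costs about 3 points of power given a drop

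*SAP*

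**What the plan says.** The final test combines the two stages by an inverse-normal function with weights 0.5 and 0.5, inside a closed testing scheme for H1 (Dose 1) and H2 (Dose 2). A dose is declared effective only if its own composite p-value (r1 or r2) and the composite for the joint null (r12) both meet the level. SAP 6.5.7 states that "the Hochberg procedure will be applied within each stage", giving p12 = min(2p(1), p(2)) in Stage 1 and the same form for q12 in Stage 2.

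For a dropped dose, the SAP says that "if a certain dose is dropped due to futility at Interim Analysis, the corresponding p-values in Stage 2 is automatically set to 1". It illustrates this with Dose 1 dropped, where "the larger ordered p-value will be equal to 1", and Table 5 therefore gives q12 = min(2·q2, 1). Protocol 10.1.4, Table 3, is identical. The stated purpose is to ensure that the null hypothesis of a dropped dose can never be rejected.

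SAP 6.5.6 governs the Stage 2 sample size after a drop: "subjects who were planned to be enrolled in that arm after Interim Analysis will be re-distributed to the remaining treatment arms". If the retained dose has conditional power between 36% and 80%, Table 2 (Case 4, mirrored in Case 5) adds that "Sample size in Dose 2 and Placebo groups will be increased to achieve the conditional power of at least 90" per cent, with total size capped at double.

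**The concern.** The stated purpose is met without the doubling. H1 can be rejected only if r1 = c(p1, q1) meets the level, and with q1 = 1 it never does. Carrying the same 1 into the intersection does something else: it makes the retained dose pay a two-comparison penalty in a stage that contains one comparison.

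That penalty is not needed for error control. If H1 and H2 are both true then H2 is true, so q2 is by itself a valid Stage 2 p-value for the joint null, whatever Stage 1 rule led to the drop. The two-dose adjustment for Stage 1 is already in p12. What is at stake is power for the surviving dose. If only one dose works, a drop is the usual course of the trial.

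**Working it through.** **Design reproduced.** Noether's formula for the Wilcoxon test, n per arm = (1.960 + 1.2816)² / [6(P − 0.5)²] with P = Φ(δ/(σ√2)):
- SAP 3.5, δ = 15, σ = 27.3: P = 0.651, n = 76.6, so 77 (stated 77).
- δ = 15, σ = 34.83: P = 0.620, n = 122.4 (stated 122).

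**Interim boundaries.** With equal stages, the SAP 6.5.5 formula reduces to CP = Φ(2Z − 1.960√2), Z being the Stage 1 statistic. CP = 10% at Z = 0.745, 36% at Z = 1.207 and 80% at Z = 1.807.

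**One worked case.** Retained dose Z = 1.5 (p2 = 0.0668), dropped dose Z = 0 (p1 = 0.5):
- p12 = min(0.1336, 0.5) = 0.1336, normal score 1.109.
- For r12 ≤ 0.025, the Stage 2 intersection score must be at least 1.960√2 − 1.109 = 1.66, so q12 ≤ 0.048.
- Plan (q12 = 2·q2): q2 ≤ 0.024. Without doubling (q12 = q2): q2 ≤ 0.048.
- The dose's own test r2 needs only a score of 2.772 − 1.5 = 1.272, so q2 ≤ 0.102.

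The intersection is therefore the binding hurdle either way, and the doubling halves the room left.

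**Simulation.** Inputs: shared placebo arm; one-sided 0.025 scale; drift per stage (1.960 + 1.2816)/√2 = 2.292 at 90% power, or 1.981 at 80%. After a drop, Stage 2 arms are 1.5 times planned (SAP 6.5.6). If 36% < CP ≤ 80%, they are max(1.5, min(need, 3.0)) times planned, where need = ((1.960√2 − Z + 1.2816)/Z)². The 3.0 is the SAP cap, 2(n1 + n2) − n1 = 3·n1 at equal stages. The trial rejects if both c(p12, q12) and c(p2, q2) are at or below 0.025.

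Power of the retained dose given a drop:

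| Scenario | Plan | q12 = q2 | Loss (points) |
|---|---|---|---|
| Dropped dose null, 90%-power effect, SAP rules | 91.7% | 95.1% | 3.4 |
| of which retained CP 10–36% (10% of drops) | 60.2% | 69.3% | 9.1 |
| of which retained CP 36–80% (22%) | 94.7% | 97.4% | 2.7 |
| of which retained CP above 80% (68%) | 95.6% | 98.3% | 2.7 |
| Protocol 10.1.3 re-estimation target of 80% | 90.6% | 94.4% | 3.8 |
| Redistribution only, no re-estimation | 88.5% | 92.9% | 4.4 |
| Both doses effective | 85.9% | 90.6% | 4.7 |
| Dropped dose null, 80%-power effect | 82.5% | 88.6% | 6.2 |

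(The last loss is taken before rounding: 0.8862 − 0.8247.) In the first scenario r2 alone is passed in 97.6% of drops.

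**Over all trials.** One dose null: 0.7126 × 0.0337 = 0.0240. Both effective: 0.0448 × 0.0471 = 0.0021 per dose.

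**At the documents' own arm sizes** (normal approximation to the Wilcoxon test, other dose null), the loss given a drop is 2.9 points for 15/27.3 with 77 per arm, 3.1 for 15/34.83 with 122, and 2.8 for 11.51/27.3 with 132. If two-sided p-values are combined at 0.05, as 6.5.7 literally reads, it is 3.7 to 4.1.

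**Error.** Global-null family-wise error, including trials with no drop, is 0.0161 under the plan and 0.0210 without the doubling. If the worse dose were always dropped, the figures are 0.0115 and 0.0232. All are below 0.025.

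**The case against.** The strongest reply is that nothing here is an error. The rule is deliberate, explained and tabulated identically in both documents, and it controls error. Table 5 is simply Table 4 with q1 = 1, a legitimate convention that keeps a fixed two-hypothesis family in each stage. This stands: the point is about efficiency only.

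Second, the overall loss can be small. The sample size assumes one common effect for both doses, and protocol 1.3 reports that the low and medium dose groups both beat placebo in Phase 2b. If both doses work, each is dropped in only about 4.5% of trials, and the loss is 0.2 points per dose. The overall loss also depends on how conditional power is defined. Protocol 10.1.3 can be read as using the assumed effect rather than the observed trend. A null dose is then dropped in about 21% of trials, and the overall loss is roughly 1 point (0.9 to 1.2, depending on whether the re-estimation increase is applied), with 4.3 to 5.8 points given a drop. The SAP formula supersedes, but the range should be known.

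Third, subjects already on a dropped dose continue into Stage 2 (SAP Table 2, Cases 2 and 3), which the simulation ignores. The decimals are therefore approximate. This does not affect the validity of q2.

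Fourth, and most serious, is timing. The SAP change log describes "changes in the sample size and randomization scheme after the planned interim analysis", version 1.0 of the SAP went to FDA, and the interim letter tells two sponsor executives which case applies. A change now would loosen the primary test with any drop decision already known. That is formally permissible while Stage 2 is blinded, but it has a credibility cost, and it limits the recommendation.

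**Conclusion.** The concern holds as a loss of efficiency, not a Type I error defect. Once a dose is dropped, doubling the survivor's Stage 2 p-value protects nothing that r1 and p12 do not already protect. The cost given a drop is about 3 points when the dropped dose is null and the survivor has its 90%-power effect, and about 3 to 6 points over the other scenarios in the table. It is largest, about 9 points, when the survivor's conditional power is 10–36%, because the SAP then adds no re-estimation increase. Over all trials, at the 90%-power effect and with the SAP's observed-trend conditional power, it is 2.4 points with one null dose and 0.2 per dose with both effective. These figures assume equal stages, normal test statistics, a shared placebo arm and directional p-values at 0.025.

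**What to change.** In SAP 6.5.7 Table 5 and protocol 10.1.4 Table 3, replace the row for the joint null and state:

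> If one dose is dropped, no Stage 2 comparison is made for it. The Stage 2 p-value for H1∩H2 is then that of the retained dose (q12 = q2 if Dose 1 is dropped, q12 = q1 if Dose 2 is dropped). The Stage 2 p-value for the dropped dose's own hypothesis is 1.

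Leave p12, the weights and the rejection rules unchanged. State in the same place whether the p-values combined are one-sided at 0.025 (as in 6.5.5) or two-sided at 0.05 (as in 6.5.7).

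The change needs no patients, gives up no claim and keeps family-wise error below 0.025. Its cost is procedural. It alters the primary test, and protocol 6.1 says: "If changes to principal features stated in the protocol are required, these will be documented in a protocol amendment". It should therefore be made only by documented SAP and protocol amendment before any Stage 2 unblinding, with its date relative to the interim and the sponsor's knowledge of the interim decision both disclosed. If that is not possible, keep the current rule, which is valid.

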7 STATISTICAL ANALYSIS

7.1 *Analysis Populations*

The population of “all enrolled subjects” consists of all those screened subjects who meet the requirements for study participation and are entered in the Baseline period (i.e., distributed IA diary) of the study. The population of “all randomized subjects” consists of all those enrolled subjects who complete the Baseline Period, meet the inclusion/exclusion criteria and are randomized.

7.1.1 *Safety Population*

The safety population will include all randomized subjects who received at least 1 dose of study drug and have at least one post-randomization safety measurements.

7.1.2 *Intent-to-treat (ITT) Population*

The intent-to-treat population will include all subjects who received at least 1 dose of study drug and have a baseline and at least 1 valid post-randomization assessment of frequency of IA behaviors based on IA diary entry. Subjects will be analyzed according to the treatment to which they were randomized.

7.1.3 *Per Protocol (PP) Population*

The per protocol population will include all of the subjects in the ITT population who completed the treatment period (Completed Maintenance Visit 6) with 70% diary completion compliance and who did not have major protocol deviations. Diary compliance is calculated as

$$\text{diary compliance} = \frac{\text{number of days diary completed within the treatment period}}{\text{Number of treatment days}} \times 100\%$$

Detailed specification of the PP population will be provided prior to the database lock for the final analysis.

7.2 *Disposition of Subjects*

Subject disposition and reasons for screening failure will be summarized for screen-failed subjects (Table 14.1.1).

Subject randomization schedule will be listed. Subjects whose randomization codes are unblinded during the conduct of the study will be listed along with the reason for un-blinding (Listing 16.1.7).

The following summaries and listings will be based on all randomized subjects.

Subjects (n and %) who completed and discontinued from the study will be tabulated by the treatment group for (1) Randomized, (2) ITT, (3) Safety, and (4) PP populations (Table 14.1.2a – Table 14.1.2d). The primary reasons for study discontinuation will be included in the tabulation. The primary reasons may include any of the following:

- Subject withdrew consent
- Lost to follow-up
- Administrative reason
- Adverse event
- Investigator decision
- Failure to follow required study procedures
- Other

In addition, subject disposition will be summarized by treatment period (combined titration and maintenance, titration, maintenance, and tapering) for (1) Randomized, (2) ITT, (3) Safety, and (4) PP populations (Table 14.1.3a – Table 14.1.3d).

In addition, subject's enrollment will be summarized by study site among ITT population (Table 14.1.4).

A data listing will be presented for subjects who do not complete the treatment along with the reasons for discontinuation (Listing 16.2.1.1).

7.3 *Protocol Deviations*

Protocol deviations will include, but are not limited to

- Non-compliance with any scheduled study visit
- Non-compliance with study treatment
- Prohibited medications
- Non-compliance with study inclusion or exclusion criteria
- Non-compliance with study assessment procedures

Subjects with major protocol deviations will be listed based on all randomized subjects. The listing will include a brief description of the deviation, deviation category, and if applicable, study day when deviation occurred along with other pertinent information (Listing 16.2.1.2).

If warranted, subjects (n and %) with major protocol deviations will be tabulated by treatment group and deviation category (Table 14.1.5a).

Additionally, subjects (n and %) in each analysis population with major protocol violations will be tabulated by treatment group (Table 14.1.5b). Subject's inclusion/exclusion from each analysis population will be listed along with the applicable reasons for exclusion (Listing 16.2.1.3).

Summary (n and %) of the analysis population will also be presented by treatment groups for the randomized population (Table 14.1.6).

7.4 *Demographics and Baseline Subject Characteristics*

Subject age, sex, ethnicity, race, height at screening, weight at screening and baseline will be summarized based on the ITT, Safety and PP populations by treatment group. Age will be summarized as a continuous variable as well as a categorical variable (6 to 9 [i.e., <10], and 10 to 12 [i.e., ≥10 and ≤ 12] years, inclusive) (Table 14.1.7a – Table 14.1.7c).

All demographic and baseline characteristics will be included in the subject data listing (Listing 16.2.1.4).

